### **6.3.2.3. Mean FRI Index Score**

The mean FRI Index score will be calculated per the scoring algorithm in the FRI Index user's manual.

The mean FRI Index score will be summarized and analyzed in a similar fashion as the primary efficacy endpoint using MMRM described in Section 6.2.2. The model will include treatment (PM, PEOM, Sham), presence of CNV in the fellow eye (yes or no), and baseline GA lesion area ( $< 7.5$  mm^2 or  $\geq 7.5$  mm^2) as fixed effects; baseline mean FRI Index score and baseline study eye status (Better-seeing Eye vs. Worse-seeing Eye) as covariates, time (in months) as a factor; the time  $\times$  treatment interaction term as well as the baseline mean FRI Index score  $\times$  time interaction term.

The observed values for the mean FRI Index score will be summarized by treatment group and visit. Summaries will present the descriptive statistics for baseline, absolute values and change from baseline data.

The mean change from baseline in the mean FRI Index score  $\pm$  the standard error as well as the LS mean of the change from baseline in the mean FRI Index score  $\pm$  the standard error will be plotted over time by treatment group.

In addition, the mean FRI Index score will be converted to the FRI Level variable, as per the user manual, ranging from 1 (Unable to do) to 4 (Totally independent). The categorical changes from baseline (improvements (an increase in FRI level), minimal/no change (no change in FRI level), and worsening (decrease in FRI level)) will be summarized by treatment group and visit.

The shift from baseline in the FRI level over time will be presented by treatment group.

All FRI data will be listed for the ITT set.

#### **6.3.2.4. NL-BCVA Score**

The mean NL-BCVA score for the study eye will be summarized and analyzed in a similar fashion as the primary efficacy endpoint using MMRM described in Section 6.2.2. The model will include treatment (PM, PEOM, Sham), presence of CNV in the fellow eye (yes or no), and baseline GA lesion area ( $< 7.5 \text{ mm}^2$  or  $\geq 7.5 \text{ mm}^2$ ) as fixed effects; baseline NL-BCVA score as a covariate, time (in months) as a factor; the time  $\times$  treatment interaction term as well as the baseline NL-BCVA score  $\times$  time interaction term. Note, for the second year, only timepoints that were measured for all three treatment groups will be included in the model.

The observed values for the NL-BCVA will be summarized by treatment group and visit for both the study and the fellow eye. Summaries will present the descriptive statistics for baseline, absolute values and change from baseline data.

The mean change from baseline in the NL-BCVA score for the study eye  $\pm$  the standard error as well as the LS mean of the change from baseline in the NL-BCVA score for the study eye  $\pm$  the standard error will be plotted over time by treatment group.

In addition, the categorical changes (improvements of  $\geq 15$ ,  $\geq 10$  to  $< 15$ ,  $\geq 5$  to  $< 10$ , and minimal/no change ( $-4$  to  $4$ ), worsening of  $\geq 5$  to  $< 10$ , and  $\geq 10$  to  $< 15$  and  $\geq 15$ ) for the study eye will be summarized by treatment group and visit.

The shift from baseline in the NL-BCVA of the study eye categories ( $\geq 70$ ,  $\geq 60 - < 70$ ,  $\geq 35 - < 60$ ,  $\geq 20 - < 35$ ,  $< 20$  ETDRS letters over time will be presented by treatment group and visit.

The above-mentioned ETDRS letter thresholds are based on WHO definitions for vision impairment and blindness. WHO criteria were implemented in an attempt to capture the progressive nature of Geographic Atrophy and the ultimate treatment goal of avoiding successive vision impairment and blindness through application of active treatment (Pegcetacoplan vs. Sham).

The average NL-BCVA score over the last 3 months for each reporting period (Month 10 - Month 12 for the Month 12 reporting; Month 22 - Month 24 for the Month 24 reporting) will be calculated for each subject who has at least one NL-BCVA assessment in these windows. The observed values for the NL-BCVA and changes from baseline will be summarized by treatment group for the study eye. Summaries will present the descriptive statistics for baseline, absolute values and change from baseline data.

All NL-BCVA data will be listed for the ITT set.

#### **6.3.3. Sensitivity Analyses of Key Secondary Efficacy Endpoints**

The missing data analyses based on imputation described in Section 6.2.3.1 will be repeated for the key secondary efficacy endpoints at the time of the final study analysis for the full 24 months only. The key secondary endpoints will also be analyzed without pooling the two sham arms (SM and SEOM) for the full 24 months only.

In addition, to assess the potential effect of different assessment tools, the main analysis of monocular maximum reading speed will be repeated by reading chart type.

---

 approximated from 6/18; see <https://icd.who.int/browse11/l-m/en#/http://id.who.int/icd/entity/1103667651>

Maximum reading speed with adjustment for reading inaccuracy will also be analyzed, only in the study eye, for the first 12 months as well as the full 24 months.

#### **6.3.4. Supplementary Analyses of Key Secondary Efficacy Endpoints**

The supplementary analyses described for the primary endpoint in Section 6.2.4.1 and Section 6.2.4.2 will also be performed for the key secondary endpoints for the first 12 months as well as the full 24 months.

In addition, the analysis of mean threshold sensitivity of all points will be repeated for the study eye excluding data not of acceptable quality for either the main or supplementary analysis, as identified by the reading center, per the Imaging Charter or where the fixation loss was > 20%. This analysis will be performed for the first 12 months as well as the full 24 months.

#### **6.3.5. Subgroup Analyses of Key Secondary Efficacy Endpoints**

The subgroup analyses of the key secondary endpoints will be performed for the full 24 months. Select subgroup analyses of the key secondary endpoints may be performed at Month 12, if necessary, to support regulatory filings. The subgroups evaluated for key secondary endpoints will be the same as evaluated for the primary efficacy endpoint (see Section 6.2.5).

In addition, the following subgroup analyses will be performed:

##### Monocular Maximum Reading Speed

- Study eye baseline monocular maximum reading speed (<60, 60-<160, ≥160)
- Study eye fixation stability (95% BCEA) categories (approximately tertiles)

##### Mean FRI Index score

- Baseline Study Eye Status (Better-seeing Eye vs. Worse-seeing Eye)
- Study eye fixation stability (95% BCEA) categories (approximately tertiles)

##### NL-BCVA

- Study eye fixation stability (95% BCEA) categories (approximately tertiles)

For each endpoint, a MMRM similar to that specified for the main analysis of the key secondary endpoints (Section 6.3.2) will be used for each subgroup analysis based on the data subset for the subject subgroup of interest. Baseline covariates included in the main analysis but no longer relevant given the subgroup of interest will be excluded from the model. The estimated treatment effects (PM vs. Sham or PEOM vs. Sham) and corresponding 95% CIs and p-values from the models will be displayed graphically for each pegcetacoplan arm and each level of the subgroups specified (e.g. via forest plots).

#### **6.4. Analyses of Other Secondary Efficacy Endpoints**

The secondary efficacy endpoints are listed in Section 2.2.3. At the time of the Month 12 reporting, all secondary efficacy endpoints will be evaluated based on data from baseline to Month 12 (see Section 3.5). For the Month 12 analyses, post-baseline visits, up to and including Month 12, will be included. At the time of the final study analysis, all secondary efficacy

endpoints will be evaluated based on data from baseline to Month 24. For the Month 24 analyses, post-baseline visits, up to and including Month 24, will be included.

Unless otherwise specified, all secondary efficacy endpoints will be analyzed for the mITT set.

#### **6.4.1. Low Luminance Best-Corrected Visual Acuity (LL-BCVA)**

LL-BCVA of the study eye will be summarized and analyzed in the similar fashion as the primary efficacy endpoint using MMRM described in Section 6.2.2. The model will include treatment (PM, PEOM, Sham), presence of CNV in the fellow eye (yes or no), and baseline GA lesion area ( $< 7.5 \text{ mm}^2$  or  $\geq 7.5 \text{ mm}^2$ ) as fixed effects; baseline LL-BCVA score as a covariate, time (in months) as a factor; the time  $\times$  treatment interaction term as well as the baseline LL-BCVA score  $\times$  time interaction term. Note, for the second year, only timepoints that were measured for all three treatment groups will be included in the model.

The observed values for the LL-BCVA will be summarized by treatment group and visit for both the study and the fellow eye. Summaries will present the descriptive statistics for baseline, absolute values and change from baseline data.

The mean change from baseline in the LL-BCVA score in the study eye  $\pm$  the standard error as well as the LS mean of the change from baseline in the LL-BCVA score in the study eye  $\pm$  the standard error will be plotted over time by treatment group.

The categorical changes (improvements of  $\geq 15$ ,  $\geq 10$  to  $< 15$ ,  $\geq 5$  to  $< 10$ , and minimal/no change ( $-4$  to  $4$ ), worsening of  $\geq 5$  to  $< 10$ , and  $\geq 10$  to  $< 15$  and  $\geq 15$ ) for the study eye will be summarized by treatment group and visit.

Additionally, the average LL-BCVA score over the last 3 months for each reporting period (Month 10 - Month 12 for the Month 12 reporting; Month 22 - Month 24 for the Month 24 reporting) will be calculated for each subject who has at least one LL-BCVA assessment in these windows. The observed values for the LL-BCVA and changes from baseline will be summarized by treatment group for the study eye. Summaries will present the descriptive statistics for baseline, absolute values and change from baseline data.

The same subgroup analyses as described for NL-BCVA in Section 6.3.5 will also be repeated for LL-BCVA for the full 24 months.

All LL-BCVA data will be listed for the ITT set. In addition, the low luminance deficit will be calculated as the difference between NL-BCVA and LL-BCVA and listed for the ITT set.

#### **6.4.2. Total Area of GA lesion(s) at each planned assessment**

The change from baseline at each planned assessment (other than Month 12 and Month 24) in the total area of GA lesion(s) in the study eye, as assessed by FAF, will be estimated from the MMRM analyses described in Section 6.2.2.

#### **6.4.3. Monocular critical print size**

Critical print size will be calculated as the smallest print size which support reading speed at 80% of the maximum reading speed, without adjustment for reading inaccuracy (Baskaran et al. 2019).

Monocular critical print size of the study eye will be summarized and analyzed in a similar fashion as the primary efficacy endpoint using MMRM described in Section 6.2.2. The model will include treatment (PM, PEOM, Sham), presence of CNV in the fellow eye (yes or no), and baseline GA lesion area ( $< 7.5 \text{ mm}^2$  or  $\geq 7.5 \text{ mm}^2$ ) as fixed effects; baseline monocular critical print size as well as the chart type (MNRead or Radner) as covariates, time (in months) as a factor; the time  $\times$  treatment interaction term as well as the baseline monocular critical print size  $\times$  time interaction term.

The observed values for the monocular critical print size will be summarized by treatment group and visit for both the study and the fellow eye. Summaries will present the descriptive statistics for baseline, absolute values and change from baseline data.

To assess the potential effect of different assessment tools, the analysis of monocular critical print size will be repeated by chart type.

All monocular critical print size data will be listed for the ITT set.

#### **6.4.4. NEI VFQ-25 Distance Activity Subscale Score**

NEI VFQ-25 distance activity subscale score will be calculated per the scoring algorithms in user's manual.

NEI VFQ-25 distance activity subscale score will be summarized and analyzed in a similar fashion as the primary efficacy endpoint using MMRM described in Section 6.2.2. The model will include treatment (PM, PEOM, Sham), presence of CNV in the fellow eye (yes or no), and baseline GA lesion area ( $< 7.5 \text{ mm}^2$  or  $\geq 7.5 \text{ mm}^2$ ) as fixed effects; baseline NEI VFQ-25 distance activity subscale score and baseline study eye status (Better-seeing Eye vs. Worse-seeing Eye) as covariates, time (in months) as a factor; as well as the time  $\times$  treatment interaction term as well as the baseline NEI VFQ-25 distance activity subscale score  $\times$  time interaction term.

The observed values for the NEI VFQ-25 distance activity subscale score will be summarized by treatment group and visit. Summaries will present the descriptive statistics for baseline, absolute values and change from baseline data.

The categorical changes (improvements of  $>5$  units and minimal/no change ( $-5$  to  $5$ ), worsening of a decrease of  $>5$  units) will be summarized by treatment group and visit.

In addition, the shift from baseline in NEI VFQ-25 distance activity subscale score categories ( $>80$ ,  $>65 - \leq 80$ ,  $>50 - \leq 65$ ,  $\geq 35 - \leq 50$ ,  $<35$ ) will be summarized by treatment group and visit.

All NEI VFQ-25 data will be listed for the ITT set.

#### **6.4.5. Macular Functional Response based on Microperimetry**

The number of scotomatous points will be determined from the mesopic microperimetry as an assessment of the macular functional response.

Number of scotomatous points in the study eye will be summarized and analyzed in a similar fashion as the primary efficacy endpoint using MMRM described in Section 6.2.2. The model will include treatment (PM, PEOM, Sham), presence of CNV in the fellow eye (yes or no), and baseline GA lesion area ( $< 7.5 \text{ mm}^2$  or  $\geq 7.5 \text{ mm}^2$ ) as fixed effects; baseline number of

scotomatous points as a covariate, time (in months) as a factor; the time × treatment interaction term as well as the number of scotomatous points × time interaction term.

The observed values for number of scotomatous points will be summarized by treatment group and visit for both the study and the fellow eye. Summaries will present the descriptive statistics for baseline, absolute values and change from baseline data.

The mean change from baseline for number of scotomatous points in the study eye ± the standard error as well as the LS mean of the change from baseline for number of scotomatous points in the study eye ± the standard error will be plotted over time by treatment group.

The analysis described above will also be repeated for the change from baseline in the mean threshold sensitivity of perilesional points over time.

Data not of acceptable quality for the main analysis, as identified by the reading center as per the Imaging Charter, will not be included in these analyses.

## 6.5. Multiplicity Adjustment

No hypothesis testing of the (non-key) secondary endpoints will be performed. Control of Type I error for (non-key) secondary endpoints is not applicable.

## 6.6. Analyses of Exploratory Endpoints

The exploratory efficacy endpoints are listed in Section 2.2.4. At the time of Month 12 reporting, all exploratory efficacy endpoints will be evaluated based on data from baseline to Month 12 (see Section 3.5). For the Month 12 analyses, post-baseline visits, up to and including Month 12, will be included. At the time of the final study analysis, all exploratory efficacy endpoints will be evaluated based on data from baseline to Month 24. For the Month 24 analyses, post-baseline visits, up to and including Month 24, will be included.

Unless otherwise specified, all exploratory efficacy endpoints will be analyzed for the mITT set.

### 6.6.1. Other Microperimetry Endpoints

In addition to the analyses performed in Sections 6.3.2.1, 6.3.2.4, and 6.4.5, the following analyses will be performed for microperimetry.

- Change from baseline in the fixation stability (95% BCEA) over time.
- Change from baseline in the mean threshold sensitivity of paralesional points over time.
- Change from baseline in the mean threshold sensitivity of extralesional points over time.
- Number of points with a clinically significant progression (number of points with a  $\geq 4$  dB decrease from baseline for points  $\geq 3$  dB at baseline) over time.

These endpoints except for the last endpoint in the study eye will be summarized and analyzed in a similar fashion as the primary efficacy endpoint using MMRM described in Section 6.2.2.

The model will include treatment (PM, PEOM, Sham), presence of CNV in the fellow eye (yes or no), and baseline GA lesion area ( $< 7.5$  mm^2 or  $\geq 7.5$  mm^2) as fixed effects; the baseline

value of the endpoint as a covariate, time (in months) as a factor; as well as the time  $\times$  treatment interaction term as well as the baseline value of the endpoint  $\times$  time interaction term.

The observed values for the endpoints will be summarized by treatment group and visit for both the study and the fellow eye. Summaries will present the descriptive statistics for baseline, absolute values and change from baseline data.

The mean change from baseline for each endpoint in the study eye  $\pm$  the standard error as well as the LS mean of the change from baseline for each endpoint in the study eye  $\pm$  the standard error will be plotted over time by treatment group.

Data not acceptable quality for the main analysis as identified by the reading center per the Imaging Charter, will not be included in these analyses.

### **6.6.2. NEI VFQ-25 and NEI VFQ-39 Additional Analyses**

Descriptive summary statistics for baseline, absolute values and change from baseline data will be provided by treatment group and visit for the following NEI VFQ-25 and NEI VFQ-39 scores:

- NEI VFQ-39 distance activity subscale
- NEI VFQ-25 composite score
- NEI VFQ-39 composite score
- NEI VFQ-25 near activity subscale score
- NEI VFQ-39 near activity subscale score
- NEI VFQ-25 driving subscale score (for subjects who are currently driving at baseline)

The shift from baseline in NEI VFQ score categories ( $>80$ ,  $>65 - \leq 80$ ,  $>50 - \leq 65$ ,  $\geq 35 - \leq 50$ ,  $<35$ ) will be summarized by treatment group and visit for the scores described above.

In addition, the categorical changes (improvements of  $>5$  units and minimal/no change ( $-5$  to  $5$ ), worsening of a decrease of  $>5$  units) will be summarized by treatment group and visit for the following NEI VFQ-25 Scores: Composite and Near Activity.

For the NEI VFQ-25 Driving subscale score, the number and percentage of subjects with a worsening driving outcome compared to baseline will be summarized by treatment group and visit. Each visit will display the number of patients who were driving at baseline with at least one of the worsening driving outcomes. The categories to determine worsening driving outcomes are: conversion to no longer currently driving, increase in difficulty driving in familiar places in daytime, increase in difficult driving at night or stopped doing this due to vision, increase in difficulty driving in difficult conditions or stopped doing this due to vision.

All NEI VFQ-25 data will be listed for the ITT set.

### **6.6.3. Binocular Maximum Reading Speed and Critical Print Size**

Descriptive summary statistics for baseline, absolute values and change from baseline data will be provided by treatment group and visit for the binocular maximum reading speed and critical

print size with no adjustment for reading inaccuracy. All binocular maximum reading speed and critical print size data will be listed for the ITT set.

Categorical changes over time and categorical shifts from baseline will be presented, as will be done for the monocular reading speed.

#### **6.6.4. GA Lesion (s) Study Eye to Fellow Eye Comparisons**

Descriptive summary statistics will be provided by treatment and visit for the change from baseline in total area of GA Lesion(s) for the study eye as well as for the fellow eye in subjects with bilateral GA with fellow eyes that satisfy the following characteristics at baseline:

- Absence of CNV in the medical history
- Baseline GA lesion size between 2.5 and 17.5 mm^2
- Presence of any pattern of hyperautofluorescence in the junctional zone of GA
- GA not confluent with any peripapillary atrophy

The change from baseline in total area of GA Lesion(s) ± the standard error in the study eye as well as the fellow eye will be plotted over time by treatment group for the subjects with bilateral GA with fellow eyes that satisfy the above characteristics.

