12.7.3. Exploratory Efficacy Analysis

Summary statistics will be provided for the following exploratory endpoints:

- Change from baseline in NEI VFQ-25 composite score at Month 12 and Month 24.
- Change from baseline in NEI VFQ-25 near activity subscale score at Month 12 and Month 24 (in select countries).
- Comparison between study eye and fellow eye in change in GA lesion size from baseline to Month 12 and Month 24.
- Binocular maximum reading speed as assessed by MNREAD or Radner Reading Charts over time (in select countries).
- Binocular critical print size as assessed by MNREAD or Radner Reading Charts over time (in select countries).
- Relationship between genetic polymorphisms associated with AMD with GA progression and response to pegcetacoplan.
- Incidence of new onset of subclinical CNV in the study eye.
- Assess sensitivity and specificity of a digital reading speed application to detect disease progression / regression (optional, select sites).
- Assess sensitivity and specificity of a digital visual function application to detect disease progression / regression (optional, select sites).

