G. Only subjects that sign the separate consent for the clinical repository and genotyping will have these samples collected. A 14-mL whole-blood sample will be collected at each of the specified visits.

- H. Blood pressure, respiratory rate, heart rate, and temperature. On dosing days, vital signs should be taken predose.
- I. Height and weight should be collected at screening.
- J. Perform assessments prior to dilating the eyes.
- K. In select countries, the MNREAD or Radner Reading Charts should be done during the study visit, prior to dilating the eyes. It should be performed monocularly first, then binocularly.
- L. Microperimetry assessments will be performed post dilation. Data will be forwarded to the reading center.
- M. To be administered by the masked site staff prior to any other assessments performed on that day. In-clinic assessments on the digital application should be completed after completion of all functional tests and quality of life measures prior to dilating the eyes.
- N. At select sites, and for those subjects who decide to participate, the digital applications will be completed on an electronic device and will consist of assessments for visual function and reading speed. Subjects will receive training at Day 1 on the use of the digital applications and the electronic device and will perform the tests using the application in the clinic at Month 1, Month 2, Month 3, Month 6, Month 12, Month 18, and Month 24. Beginning at Day 1, subjects will complete the functional assessments weekly at home. Subjects should be instructed to complete the assessments on the same day each week and at approximately the same time of day each week, if possible.
- O. FAF and SD-OCT images, near infrared reflectance, fluorescein angiograms, and fundus photographs will be performed for the study eye only on days where 'SE' is specified and for both eyes at all other visits as specified in the above schedule and will be sent to the reading center for evaluation (consult the reading center manual for specifics on image capture, processing, and transmission). Images should be captured prior to dosing on dosing days. If a subject misses a study visit or images cannot be obtained at a specific visit, study staff should make every effort to obtain images at the next scheduled visit. If new active CNV is suspected, SD-OCT, FFA and OCT-A (select sites) images must be collected and sent to the reading center for analysis.

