#### **2.2.4. Exploratory Endpoints**

- Additional microperimetry endpoints including:
  - Change from baseline in fixation stability (95% bivariate contour ellipse area (BCEA)) over time.
  - Change from baseline in the mean threshold sensitivity of points beyond 500 microns outside the atrophy border (paralesional points) over time.
  - Change from baseline in the mean threshold sensitivity of points beyond the GA lesion (extralesional points) over time.
  - Number of points with clinically significant progression over time, defined as a decrease of more than 4 dB.
- Additional NEI-VFQ endpoints including:
  - Change from baseline in the NEI VFQ-39 distance activity subscale score (in select sites) over time.
  - Change from baseline in NEI VFQ-25 composite score over time.
  - Change from baseline in NEI VFQ-39 composite score over time.
  - Change from baseline in NEI VFQ-25 near activity subscale score (in select countries) over time.
  - Change from baseline in NEI VFQ-39 near activity subscale score (in select countries) over time.
  - Change from baseline in NEI VFQ-25 driving subscale score (in select countries) over time as well as the number and percentage of subjects with worse driving outcomes for subjects who are currently driving at baseline.
- Difference between study eye and fellow eye in change in GA lesion size from baseline over time in subjects with bilateral GA.

- Change from baseline in binocular maximum reading speed as assessed by MNRead or Radner Reading Charts (in select countries) over time.
- Change from baseline in binocular critical print size as assessed by MNRead or Radner Reading Charts (in select countries) over time.
- Change from baseline in digital reading index (in select sites) over time as measured by the Spotlight instrument.
- Change from baseline in digital visual function (metamorphopsia) (in select sites) over time as measured by the Alleye instrument.
- Progression from incomplete retinal pigment epithelium and outer retinal atrophy (iRORA) to complete retinal pigment epithelium and outer retinal atrophy (cRORA).
- Progression from large drusen to iRORA or cRORA.
- Other efficacy imaging endpoints including change in the distance of the atrophy junction to the fovea, and non-subfoveal atrophy to subfoveal atrophy conversion.

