### For key secondary, secondary, and exploratory endpoints

- Presence of CNV in the fellow eye (yes; no)
- Baseline GA lesion area ( $< 7.5 \text{ mm}^2$  or  $\geq 7.5 \text{ mm}^2$ )
- Baseline value of the endpoint

Of note, the randomization stratification factors were assessed at the screening visit. In the event of a change in status in the GA lesion area between the screening visit and the baseline visit (i.e., GA lesion area  $< 7.5 \text{ mm}^2$  at screening to  $\geq 7.5 \text{ mm}^2$ ) then the baseline status will be used.

If a statistical model is not directly specified and if necessary, data will be analyzed with the following approaches:

- For continuous endpoints, the MMRM analysis described for the primary endpoint in Section 6.2.2.
- For categorical or ordinal variables, a Cochran Mantel Haenszel (CMH) test with the baseline category status, presence of CNV in the fellow eye (yes or no), and baseline GA lesion area ( $< 7.5 \text{ mm}^2$  or  $\geq 7.5 \text{ mm}^2$ ) as stratification factors.

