### 6.2.2. Main Analysis of Primary Efficacy Endpoint

The primary endpoint will be analyzed in the mITT population with subjects grouped according to the treatment assigned at randomization.

A MMRM model will be used to analyze the primary endpoint. The analysis model will include treatment (PM, PEOM, sham), presence of choroidal neovascularization in the fellow eye at baseline (Yes, No) and baseline GA lesion area ( $< 7.5 \text{ mm}^2$  or  $\geq 7.5 \text{ mm}^2$ ) as fixed effects, time (study month, categorical) as a factor, the time  $\times$  treatment interaction term, and the baseline GA lesion area ( $< 7.5 \text{ mm}^2$  or  $\geq 7.5 \text{ mm}^2$ )  $\times$  time interaction term. The least square [LS] mean change from baseline to Month 12 will be estimated from the model for each of three arms as well as the comparisons of each of the three arms to each other. For other time points of interest, LS mean change from baseline will be estimated and compared between treatments. For each estimated LS mean, the corresponding 95% CI will be presented based on the model. For the comparison of the LS means, the corresponding 95% CI and the 2-sided P-value along with the percentage difference (difference in LS means between the arms/the comparison group LS mean) will be

presented. A common unstructured covariance matrix will be used to model the within-subject errors, the sandwich estimator (Diggle, Liang, and Zeger 1994) will be used to estimate the standard errors of the fixed effects parameters, and the degrees of freedom will be partitioned into between-subject and within-subject portions. If there are convergence problems with the model, then a heterogeneous autoregressive (1) covariance matrix will be used. If convergence problems still exist, an autoregressive (1) covariance matrix will be used. The LS mean of the change from baseline in the total area of GA lesion(s)  $\pm$  the standard error will be plotted over time by treatment group.

The observed values for the total area of GA lesion(s) will be summarized by treatment group and visit for both the study and the fellow eye. Summaries will present the descriptive statistics for baseline, absolute values and change from baseline data by visit.

The mean change from baseline in the total area of GA lesion (s) in the study eye  $\pm$  the standard error will be plotted over time by treatment group.

All GA lesion (s) size data will be listed for the ITT set.

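### SAP 2.2.4 defines a study-eye versus fellow-eye difference in lesion growth, but SAP 6.6.4 summarises each eye separately and gives that difference no SD, SE or confidence interval

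*SAP*

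**What the plan says.** The protocol (12.7.3) promises summary statistics for its exploratory endpoints, one of which is "Comparison between study eye and fellow eye in change in GA lesion size from baseline to Month 12 and Month 24". The SAP sharpens this in 2.2.4 to "Difference between study eye and fellow eye in change in GA lesion size from baseline over time in subjects with bilateral GA".

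SAP 6.6.4 is the only section devoted to the endpoint. It restricts the analysis to bilateral-GA subjects whose fellow eye meets four baseline conditions: no CNV history, lesion size within the trial's entry range, some junctional-zone hyperautofluorescence, and no joining with peripapillary atrophy. For these subjects it plans two outputs, both by treatment group:

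- a table of change from baseline "for the study eye as well as for the fellow eye in subjects with bilateral GA";
- a plot in which the change, with its standard error, "in the study eye as well as the fellow eye will be plotted over time by treatment group".

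The other place where fellow-eye lesion area appears is SAP 6.2.2, where observed values "will be summarized by treatment group and visit for both the study and the fellow eye". That too is eye by eye.

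**The concern.** A between-eye difference is a paired quantity: one number per subject, with its own spread. The four baseline conditions make the fellow eye resemble a study eye, which is useful mainly if the two eyes of one person are then compared. Section 6.6.4 stops before that step. Its title announces comparisons, but it specifies no comparison statistic.

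The practical risk lies in how the output will be read. A reader who sees two curves with separate error bars will tend to judge the gap between them as if the eyes came from different people. If growth is positively correlated between a subject's eyes, that understates how precisely the gap is known.

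**Working it through.** **No figure to reproduce.** The documents state no number for this endpoint, so the first step is to set the definition against the analysis.

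| Place | What it provides for the between-eye difference |
|---|---|
| SAP 2.2.4 | Defines it as the endpoint |
| SAP 6.6.4 | Table and plot for each eye; no difference variable |
| SAP 6.2.2 | Summary for each eye; no difference variable |
| SAP 13.5.1 and sample code | No between-eye derivation. By contrast, 13.5.6 derives another difference, the low luminance deficit |
| SAP 6, general rules | Fallback worded "If a statistical model is not directly specified and if necessary, data will be analyzed with the following approaches"; conditional, and defines no difference |
| SAP 6.6 | General statement that "all exploratory efficacy endpoints will be evaluated based on data from baseline to Month 12"; names no method |
| SAP 15 | Records that the low luminance deficit will only be listed; records nothing for this endpoint |

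**Visits at which the difference exists.** Footnote O of protocol Appendices A to D says imaging "will be performed for the study eye only on days where 'SE' is specified and for both eyes at all other visits". In the FAF row, Months 2, 4, 8, 10, 14, 16, 20 and 22 are marked study eye only. Both eyes are imaged post-baseline at Months 6, 12, 18 and 24.

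**What is lost without pairing.** Inputs:

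- SD of lesion growth: 1.50 mm², or 1.25 mm² (protocol 12.5, SAP 3.4), assumed here to apply to each eye. As a check on the 1.50, a two-group power calculation with 200 per group and alpha 0.0495 gives 99.3% and 81.7%, against the plan's 99.2% and 81.5%.
- Between-eye correlation r: not in the documents; assumed, range 0 to 0.9.
- Eligible subjects in a group: not in the documents; 100 assumed for illustration.

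Formulas:

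- SE with the eyes treated as independent = SD × sqrt(2/n)
- Paired SE = SD × sqrt(2(1-r)/n)
- Overstatement = first / second = 1/sqrt(1-r), which does not depend on SD or n

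With SD 1.50 and n = 100, the independent SE is 1.50 × sqrt(0.02) = 0.212 mm².

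| r (assumed) | Paired SE, mm² | Overstatement if treated as independent |
|---|---|---|
| 0 | 0.212 | 1.00 |
| 0.5 | 0.150 | 1.41 |
| 0.7 | 0.116 | 1.83 |
| 0.8 | 0.095 | 2.24 |
| 0.9 | 0.067 | 3.16 |

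With SD 1.25 the independent SE is 0.177 mm² and the paired SE at r = 0.5 is 0.125 mm². The ratio is again 1.41.

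**What is not lost.** The mean of per-subject differences equals the difference of the two means when the same subjects contribute both eyes. Section 6.6.4 uses one set of subjects for both eyes, so subtraction works wherever both are observed. It does not require both images at a given visit, so with missing images the two means can rest on different subjects.

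**The case against.** The strongest reply is that the plan delivers what the protocol promised. Protocol 12.7.3 commits only to summary statistics, and 6.6.4 gives them for both eyes in a sensibly restricted group. Neither document promises a test or model comparing arms on this endpoint. That stands: the missing arm comparison is not a defect.

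A second reply is that the information is not destroyed. SAP 6.2.2 and 6.6.8 list lesion-size and FAF data by subject, so the paired difference could be computed from planned listings. That is true, but a listing is not an analysis. The general rules in SAP 6 and 6.6 do not close the gap either, since they never define the variable.

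Three stronger readings are tempting, and the documents do not support them.

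- A reader might infer that the endpoint is not estimated at all. The mean difference is available by subtraction where both eyes are observed; what is missing is its precision.
- A reader might infer that the paired difference would sharpen the treatment comparison. Relative to the study eye alone in the same subjects, with equal variance in both eyes, its SE is multiplied by sqrt(2(1-r)). That is 0.775 at r = 0.7 (23% smaller), exactly 1 at r = 0.5, and 1.18 at r = 0.3 (18% larger). With r unknown and the eligible subset smaller than the full analysis set by an unstated amount, no gain can be claimed.
- A reader might infer that the 6.2.2 model can be run unchanged on the difference. It contains fellow-eye CNV status, which SAP 5.2 bases on medical history. Section 6.6.4 excludes fellow eyes with that history, so the term is constant in this subset.

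**Conclusion.** The mismatch is real and narrow. The SAP names a within-subject difference as an endpoint, plans separate summaries for each eye, and does not record the departure. The difference therefore has no reported SD, SE or CI, and the separate SEs cannot supply one without the between-eye correlation.

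The size of the distortion depends entirely on that correlation. At zero correlation there is none; over an assumed range of 0.5 to 0.8, the SE inferred from separate error bars would be 1.41 to 2.24 times too large. The finding itself needs no value of r, because it rests on comparing 2.2.4 with 6.6.4. Since the endpoint is exploratory and carries no alpha, this is a minor improvement to reporting.

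**What to change.** In SAP 6.6.4, for eligible subjects with both eyes observed at the visit, derive study-eye minus fellow-eye change from baseline at Months 6, 12, 18 and 24. Summarise it by treatment group with n, mean, SD and paired 95% CI. Keep the planned summaries and plot for each eye alongside.

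A model comparing arms is optional. If one is used, drop the fellow-eye CNV term, as SAP 6.2.5 already does for covariates that lose relevance in a subgroup, and state whether fellow-eye baseline area is adjusted for.

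If the sponsor prefers to keep only the separate summaries, reword 2.2.4 to match and record the change in SAP 15.

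The cost is one derived variable and one table, from images already scheduled. The optional model would add some specification work.
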